8.2 Data Summarization

Granular data (collected by puff) will be in a first step summarized for each subject for the parameters described in the formula in [Table 8.2](#), before deriving the descriptive statistics using the following procedure:

- First, data are averaged to a by cigarette or by cartridge basis.
- Then those average data are averaged to a by subject basis.

Philip Morris Products S.A.
P4M3 Gen 2.0, P4-PK-04-US

██████████ Statistical Analysis Plan Number CA34617

- Finally, descriptive statistics are provided by regimen and product on those “by subject average”.

Descriptive statistics (n, mean, SD, CV%, SEM, minimum, Q1, median, Q3, maximum, and 95% confidence interval) of the puffing parameters will be provided by study product. Summaries will be further stratified by Sex. Individual values will be listed.

9. AMOUNT OF NICOTINE DELIVERED FROM P4M3 GEN 2.0

9.1 Data Collection

P4M3 Gen 2.0 Cartridges will be weighed before T_0 and within 120 min after T_0 at the time points described in Table 3 to estimate the amount of nicotine delivered during product use.

The weight will be determined with a scale with an accuracy of 1 mg.

The difference in the cartridge weight from pre product use and post product use will be calculated. The amount of nicotine delivery from P4M3 Gen 2.0 will be calculated by dividing the difference in the cartridge weight [mg] by the specific density of the e-liquid [1129.2 mg/mL] multiplied by the nicotine concentration [39.5 mg/mL].

9.2 Data Summarization

Descriptive statistics (n, mean, SD, CV%, SEM, minimum, Q1, median, Q3, maximum, and 95% confidence interval) of the amount of nicotine delivered will be provided by study product. Summaries will be further stratified by Sex. Individual values will be listed.

10. SAFETY

All case report form (CRF) data will be listed by subject and chronologically by assessment time points. This will include rechecks, unscheduled assessments, and early termination.

Applicable continuous variables will be summarized using n, arithmetic mean, SD, minimum, median, and maximum.

The level of precision will be presented as follows: minimum/maximum in the same precision as in the database, mean/median in one more precision level than minimum/maximum, SD in one more precision level than mean/median, and n will be presented as an integer.

Where individual data points are missing because of dropouts or other reasons, the data will be summarized based on reduced denominators.

10.1 Disposition of Subjects

Subjects will be summarized by number of subjects screened, enrolled, enrolled and exposed to P4M3 Gen 2.0, randomized, completed, and discontinued the study with discontinuation reasons.

10.2 Demographics

Descriptive statistics will be calculated overall for continuous variables (age, weight, height, and body mass index) and further stratified by sex.

Frequency counts will be provided for categorical variables (race, ethnicity, and sex) overall and further stratified by sex.

10.3 Tobacco/Nicotine-Containing Product Use History Questionnaire

At the Screening Visit, subjects will be asked questions about their tobacco-and/or nicotine-containing product use history. The questions will capture frequency and quantity of tobacco and/or nicotine-containing product use over the past 4 weeks, and number of continuous years of cigarette smoking.

Descriptive statistics will be calculated for continuous variables overall and further stratified by sex.

Frequency counts will be provided for categorical variables overall and further stratified by sex.

10.4 Usual Brand Cigarettes Documentation

Subject's usual brand of cigarettes will be documented and frequency counts will be provided for categorical variables (brand, brand style, flavor, menthol capsule, and cigarette length) overall and further stratified by sex.

10.5 Fagerström Test for Nicotine Dependence (FTND)

Potential nicotine dependence will be assessed at the Screening Visit using the FTND in its revised version as updated in 2012 ([Fagerström, K.O., 1978, Heatherton, T.F., et al., 1991](#)).

The questionnaire consists of six questions, which have to be answered by the subject himself/herself. The total score obtained on the test permit the classification of nicotine dependence into three levels: Mild (0 to 3 points); Moderate (4 to 6 points); Severe (7-10 points) ([Fagerström, K., et al., 2012](#)).

Descriptive statistics will be calculated for FTND score by randomized product sequence and overall. In addition, frequency counts will be provided for nicotine dependence levels (mild, moderate, and severe) overall and further stratified by sex.

10.6 Medical History

All Medical History and Concomitant Disease will be coded using the Medical Dictionary for Regulatory Activities (MedDRA[®]), Version 24.0 and listed by subject.

Philip Morris Products S.A.
P4M3 Gen 2.0, P4-PK-04-US
[REDACTED] Statistical Analysis Plan Number CA34617

10.7 Adverse Events

All adverse events (AEs) occurring during this clinical trial will be coded using MedDRA®, Version 24.0. AEs will be graded based on the Common Terminology Criteria for Adverse Events (CTCAE) version 5.0.

All AEs captured in the database will be listed in by-subject data listings including verbatim term, coded term, product, severity, relationship to study product, and action; however, only product use-emergent AEs (PUEAEs) will be summarized. Adverse events after ICF and prior to the product test on Day -1 and occurred during safety FU period (after discharge from CRU to safety FU visit) will be summarized separately under admission/safety FU period.

A study product use-emergent adverse event is defined as an AE that is starting or worsening at the time of or after study product administration. An AE that occurs during the washout period between study products is considered study product use emergent to the last study product given.

If the onset time of an AE is missing and the onset date is the same as the product administration date, the AE will be considered product use-emergent to the prior and current product. If the onset time of an AE is missing and the onset date does not fall on a product administration date, the AE will be considered product use-emergent for the last product administered. If the onset date of an AE is missing, the AE will be considered product use-emergent and attributed to each product on the study, unless the onset date is known to have occurred within or between specific product periods.

All AEs will be summarized by product and overall. The number and percentage of subjects with AEs, SAEs (including deaths), and product events will be tabulated by system organ class and preferred term. Summaries will also be presented for AEs leading to product discontinuation, AEs leading to study discontinuation, AEs by relatedness to product exposure (including expectedness) and relatedness to study procedures, AEs by severity, and AE by action taken related to the product. Tabulations will be performed for both the number of subjects experiencing an event and the number of events. Subjects with product events will also be summarized.

Serious adverse events (SAEs), if present, will also be listed. Applicable narratives will be included in the CSR.

10.8 Clinical Laboratory Tests (Clinical Chemistry, Hematology, Urinalysis)

Clinical laboratory evaluations (clinical chemistry, hematology, and urinalysis) will be performed at Screening, Admission (Day -1), and at the time of discharge (Day 3) or as early termination assessments, as applicable.

Out-of-range values and corresponding recheck results will be listed. CTCAE grading will be included as well. Other lab results within this panel and time point will also be listed for this subject. Results that are indicated as CS by the PI will be listed in the table.

For all numeric laboratory values, descriptive statistics will be presented for each laboratory test by study day. Change from baseline will be summarized in a similar manner. Baseline is

Philip Morris Products S.A.
P4M3 Gen 2.0, P4-PK-04-US

██████████ Statistical Analysis Plan Number CA34617

defined as the result closest and prior to the first product administration, which may include unscheduled or recheck results. This will typically be the result collected on Admission (Day -1). Post product use unscheduled events or rechecks will not be included in summaries. Similarly, early termination results will not be included in summaries.

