3. INVESTIGATION PLAN

3.1 STUDY DESIGN

This is a single-center, randomized, controlled, open-label, crossover study to investigate the nicotine PK profiles of variants of P4M3 Gen 2.0, an electronic nicotine delivery system (ENDS), compared to cigarettes. In addition, PD effects (subjective effects and related behavioral assessments) will be evaluated to provide further insights on product evaluation. The study will be conducted with 3 periods and 6 sequences in a cross-over design.

A Screening Visit will be conducted within 28 days (Day -29 to Day -2) prior to Admission (Day -1) to the investigational site (Figure 1). The investigational site staff will do a demonstration of P4M3 Gen 2.0, without product use, during the Screening Visit.

Figure 1 Study Design

Abbreviations: CM35 = P4M3 Gen 2.0 Classic Menthol 3.5% nicotine; CA35 = P4M3 Gen 2.0 Classic Auburn 3.5% nicotine; Cig= Subjects' own cigarette smoking; P4M3 = Electronic Nicotine Delivery System P4M3 Gen 2.0

Qualified subjects will return to the investigational site for Day -1. Subjects should have fasted for at least 10 hours prior to the safety laboratory assessments. After confirmation of eligibility, subjects will be enrolled. All subjects that are not enrolled will be considered as screen failures.

Philip Morris Products S.A.
P4M3 Gen 2.0, P4-PK-04-US

██████████ Statistical Analysis Plan Number CA34617

On Day -1, enrolled subjects will perform a product test using P4M3 Gen 2.0 Classic Auburn 3.5% (CA35) variant *ad libitum* for up to 10 minutes. After the product test, subjects not willing and/or not ready to use P4M3 Gen 2.0 during the study will be discontinued from the study, will enter the 3-day Safety Follow-up and will be replaced.

Subjects willing and ready to use 2 variants of P4M3 Gen 2.0 during the study after product test will start their confinement period of 3 days. The brand of subjects' cigarettes will be recorded.

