3.3 Discontinuation of Subjects from the Study

Discontinued subjects will include both, subjects who withdraw from the study (subject's decision) and subjects who are discontinued from the study by the decision of the Investigator. A subject can only be discontinued from the study after enrollment.

Subjects will be informed that they are free to withdraw from the study at any time. Subjects will be questioned for the reason for withdrawal from the study, although they are not obliged to disclose it. If a subject withdraws from the study, he/she will be asked to confirm that he/she agrees to undertake the early termination procedures for safety assessments, and this information will be fully documented by the Investigator.

The subject will be informed that if he/she withdraws from the study, the data collected until the point of withdrawal will be maintained as part of the study data and the samples collected prior to withdrawal will be analyzed, unless the subject disagrees in writing.

When a subject is discontinued from the study, all early termination procedures (study protocol Section 9.7) will be performed unless the subject refuses to perform the assessments or the procedures have already been performed during the study day. Early termination procedures are to be performed only for subjects who have been exposed to P4M3 Gen 2.0. After the date of termination, the subject will enter into the 3-day Safety Follow-Up Period. This applies to all subjects independent of the reason of discontinuation (for example, withdrawal of consent, or at the Investigator's decision, etc.).

Subjects must be discontinued from the study for any of the following reasons:

- Withdrawal of informed consent.
- Any AE/SAE or condition (including clinically significant changes in a laboratory parameter), which at the discretion of the Investigator is not compatible with the subject's continued participation in this study.
- Positive pregnancy test (study protocol Section 8.5).
- If the Sponsor decides to prematurely terminate the study, the subject will be promptly informed by the Investigator. The Investigator should report the fact and the reason in writing to the IRB.
- Discontinuation is considered to be in the best interest of the subject or the other subjects as judged by the Investigator.

Philip Morris Products S.A.
P4M3 Gen 2.0, P4-PK-04-US

██████████ Statistical Analysis Plan Number CA34617

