- Subject is not willing and/or ready to use P4M3 Gen 2.0 after the product test at Admission (Day -1). In such a situation, the subject will be discontinued after the product test and will enter the 3-day Safety Follow-up.
- Subject uses any tobacco or nicotine-containing product different from the assigned product during confinement.

Subjects may be discontinued from the study for the following reasons:

- Non-compliance to the study procedures based on the judgment of the Investigator.
- A sufficient number of subjects are already randomized to the study sequences (study protocol Section 5.2). In this case, additional subjects (alternates) will be discontinued prior to randomization.
- Violations of eligibility criteria have been determined (study protocol Section 5.4).

Subjects who will be discontinued from the study before enrollment will be replaced. After enrollment but before randomization, subjects who will be discontinued from the study will enter the 3-day Safety Follow-Up Period and will be replaced. However, subjects discontinued after randomization will not be replaced.

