4.1.2 Safety Population

The safety population is a subset of the screened population and consists of all subjects who give informed consent, have at least one exposure to P4M3 Gen 2.0, including the product test at Admission (Day -1), and have at least one safety assessment.

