10.9 Vital Signs

Vital signs (systolic and diastolic blood pressure, pulse rate, and respiratory rate) will be measured at the Screening Visit, on Admission (Day -1), Day 1 to Day 3 (Discharge) or as early termination assessments, as applicable. All parameters will be recorded in supine position after the subject has rested for at least 5 minutes. Subjects should have abstained from using any nicotine/tobacco containing products for at least 15 minutes prior to Vital signs assessment.

The Investigator will define vital sign ranges to determine normal or abnormal results. For those results outside of the normal range, the Investigator will determine appropriate follow up including reporting of any AEs.

Descriptive statistics will be reported for vital signs measurements (blood pressure, pulse, respiration, and temperature) by period. Change from baseline will be summarized in a similar manner. Baseline is defined as the result closest and prior to the first product administration, which may include unscheduled or recheck results. This will typically be the result collected on prior to T_0 on Day 1. Post product use unscheduled events or rechecks will not be included in summaries. Similarly, early termination results will not be included in summaries.

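### Early-termination results are kept out of every lab, vital-sign, ECG and spirometry summary, so a randomized subject who stops on Day 1 or Day 2 is largely absent from the safety change-from-baseline tables

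*SAP*

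**What the plan says.** SAP 10.8 (labs), 10.10 (ECG) and 10.13 (spirometry) each state that "Similarly, early termination results will not be included in summaries". SAP 10.9 (vital signs) has the same sentence, preceded, as in the other sections, by a bar on unscheduled results: "Post product use unscheduled events or rechecks will not be included in summaries. Similarly, early termination results will not be included in summaries".

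The same sections place labs, ECG and spirometry at Screening, Day -1, and Day 3 or early termination. The shells for Tables 15.2.3.2.1 to 15.2.3.2.3, 15.2.3.4.1 and 15.2.3.6.1 show change from baseline for Day 3 only. The shell for Table 15.2.3.3.1 shows vital-sign change only for time points after Day 1.

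On who has an early-termination visit, SAP 3.3 says "Early termination procedures are to be performed only for subjects who have been exposed to P4M3 Gen 2.0", with a waiver: "unless the subject refuses to perform the assessments or the procedures have already been performed during the study day". Protocol Table 11 lists labs, urine analysis, vital signs, ECG and spirometry among the procedures.

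The tables are titled Safety Population, which SAP 4.1.2 defines as consenting subjects who "have at least one exposure to P4M3 Gen 2.0, including the product test at Admission (Day -1), and have at least one safety assessment".

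Protocol 12.6.6 plans the change-from-baseline tables without excluding early-termination results. SAP section 11, which lists departures from the protocol's planned analysis, does not mention the exclusion.

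**The concern.** For labs, ECG and spirometry the early-termination visit stands in for Day 3. When the stand-in is excluded, a subject who stops before Day 3 has no other post-exposure value to offer, because unscheduled and recheck results are excluded too.

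Stopping need not be unrelated to the measurements. SAP 3.3 requires discontinuation for an adverse event or condition, clinically significant laboratory changes included, that the investigator judges incompatible with continuing. A subject withdrawn for a laboratory change would then be missing from the laboratory change table. Changes in ECG, vital signs, spirometry and laboratory values are named endpoints of the safety objective (Protocol 3.2), and Protocol 2.1.2 says the product has not previously been tested in humans. A reader of a table titled Safety Population would expect it to include exposed subjects whose data were collected.

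**Working it through.** The plan gives no figure to reproduce. The check is a count of what can enter the tables, followed by the share of subjects affected.

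**Step 1. Inputs**
- Scheduled post-exposure labs, ECG and spirometry: Day 3 only (SAP 10.8, 10.10, 10.13; Protocol Appendix A).
- Vital signs: before T0 on Days 1 to 3, with the Day 1 pre-T0 value as the usual baseline (SAP 10.9). Changes can therefore come only from Day 2 and Day 3.
- Day 3 safety labs are drawn in the morning before product use (Protocol 12.6.6).
- Randomized: 36, with no replacement after randomization (SAP 3.1, 3.3).

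**Step 2. Post-exposure values that can enter the change tables under the rule**

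| Randomized subject stops | Labs | ECG | Spirometry | Days with a vital-sign change |
|---|---|---|---|---|
| Day 1, after use | 0 | 0 | 0 | 0 |
| Day 2, after use | 0 | 0 | 0 | 1 (Day 2 pre-T0) |
| Day 3, after T0 but before ECG and spirometry | 1 | 0 | 0 | 1 or 2 |
| Completes | 1 | 1 | 1 | 2 |

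The Day 3 vital-sign entry depends on which reading is used, since Protocol Table 10 has one before T0 and one near discharge.

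**Step 3. Does the same-day waiver explain the zeros?** Not for labs, ECG or spirometry on Day 1 or Day 2. Protocol Tables 8 and 9 schedule none of these on those days, so they would not already have been done when the subject stopped. Only vital signs overlap.

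SAP Table 3 does give ECG windows on Days 1, 2 and 3 and on a Day 4. That does not match SAP 10.10 or Protocol Appendix A, and the passages need reconciling. The ECG shell has no column for Day 1 or Day 2, so the zeros in the table stand either way.

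**Step 4. Share affected.** Let d be the number of randomized, exposed subjects who stop before their Day 3 assessments. The share of randomized subjects missing from the Day 3 change columns is d/36. The values of d below are assumed.
- d = 0: 0/36 = 0%
- d = 1: 1/36 = 2.8%
- d = 2: 2/36 = 5.6%
- d = 4: 4/36 = 11.1%

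**Step 5. Effect on a mean.** If the d stoppers differ from the other subjects by an average of x, adding their values moves the mean by d·x/36. As an illustration with assumed inputs only, d = 2 and x = 30 ms in QTcF gives (2 × 30)/36 = 1.67 ms. If the other 34 all showed 0, the table's maximum would be 0 without the two subjects and 30 with them.

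**The case against.** The best defence is that nothing is lost from the report. SAP section 10 lists all case report form data, early-termination results included, and SAP 10.8 adds listings of out-of-range and clinically significant lab values. Protocol 8.4.1 requires post-screening lab abnormalities of grade 2 or higher, or grade 1 and clinically significant, to be recorded as adverse events or linked to one or to a concomitant disease. Protocol 8.4.2 requires other clinically significant findings to be reported as adverse events. SAP 10.7 tabulates adverse events leading to study discontinuation, and the change tables print n. This stands. A reader might infer that extreme values are hidden from the report, but the documents do not support that. They are absent only from the mean, minimum, maximum and other statistics of these tables.

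The exclusion also has a rationale. Early-termination labs may be non-fasting, whereas Day 3 labs require 10 hours of fasting (Protocol 7.6.1). The Day 3 ECG is timed at 60 ± 10 minutes after T0 (Protocol Appendix A), and an early-termination ECG has no such timing. This is a reason to show the results separately and label them. It does not justify leaving them out of every summary.

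Three other readings are tempting and go too far:
- That the rule removes subjects exposed only at the product test. They stop either because "subjects not willing and/or not ready to use P4M3 Gen 2.0 during the study will be discontinued from the study" or because "additional subjects (alternates) will be discontinued prior to randomization". Their Day -1 ECG, spirometry, vital signs and labs were scheduled before the test, so if they stop that day the waiver may mean no early-termination values exist to exclude.
- That every early stopper loses all post-exposure data. A subject stopped on Day 3 may already have that day's pre-use labs and vital signs, and both count.
- That the tables are biased towards no change. Early termination also follows withdrawal of consent or non-compliance, so the direction is plausible but not established.

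**Conclusion.** The point holds for randomized, exposed subjects who stop on Day 1 or Day 2. Under the SAP's rule they contribute no post-exposure lab, ECG or spirometry value and at most one vital-sign change to tables titled Safety Population, even though the protocol has those values collected because the subject was exposed. The exclusion is not declared in SAP section 11.

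The size rests on d, which the documents do not give. It also assumes that the early-termination assessments are actually performed, because a subject may refuse them. The study tests no hypothesis and these tables are descriptive, so the consequence is incomplete summaries of named secondary endpoints. The PK analysis and the adverse event tables are unaffected. The change is worth making because the data are potentially informative and the remedy is small.

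**What to change.** - In Tables 15.2.3.2.1 to 15.2.3.2.3, 15.2.3.3.1, 15.2.3.4.1 and 15.2.3.6.1, keep the scheduled Day 3 results as planned. Add either a separate early-termination column or row, or one for the last post-exposure value (Day 3 or early termination), each with change from baseline and its own n.
- Footnote that fasting status and time since product use differ from Day 3. The separate display keeps those conditions apart; the pooled one gives a single value per exposed subject with data.
- Limit the exclusion sentences in SAP 10.8, 10.9, 10.10 and 10.13 to the scheduled-visit columns.
- List whatever exclusion remains in SAP section 11.

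The cost is one derived visit and one extra column or row from data already collected. Day 3 results do not change. The downside is that early-termination values arise under different conditions and, with few stoppers, will be sparse. SAP section 1 allows amendments until database lock and says supplementary analyses are to be described in the study report.
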